#### 1.4.2 Anti-drug Antibody (ADA) Measurements

Immunogenicity of pegloticase will be assessed in serum samples by evaluating anti-PEG and anti-uricase immunoglobulin G (IgG) antibodies. Samples will be collected prior to the pegloticase infusion on Day 1 and at the Weeks 2, 6, 12, 20 and the End-of-study (Week 24)/Early Termination Visit and 3-month Post-Treatment Follow-up Visits. In the event of an AE suspected to be an IR, a serum sample will be collected at that time or at the subsequent visit for evaluation of pegloticase antibodies.

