A subject will be declared a non-responder if the subject had sUA level  $> 6$  mg/dL at 2 consecutive study visits beginning with the Week 2 Visit. In addition, a subject who withdraws from the study for any reason (other than meeting Individual Subject sUA Discontinuation Criteria) after the first dose of pegloticase in the pegloticase + MTX Period and prior to or during Month 6 will be considered a Month 6 non-responder if sUA values are not collected at the planned timepoints. The proportion of Month 6 responders by pegloticase baseline and post baseline ADA (positive /negative) status will be summarized similarly as the above. Please see Section 3.6.3.4 for the definition of pegloticase baseline and post baseline ADA status.

The proportion of time that the sUA level is below 6 mg/dL during Month 6 is defined as the ratio of the time during which the sUA level remains below 6 mg/dL (using linear interpolation, if necessary) to the entire time interval during Month 6. Results from visits where an infusion was not performed (e.g. subject discontinued pegloticase but remained in study) will be used when available. The subject-specific proportion of time during the period during which the sUA was less than 6 mg/dL will be summarized using descriptive statistics. If a subject has  $\leq 1$  data point in the period, then the proportion of time will not be calculated.

The number and proportion of subjects that discontinued treatment due to the stopping rule will be summarized. In addition, the number and proportion of subjects missing all data in analysis period will be summarized.

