### 3.5.2 Anti-Drug Antibodies

Immunogenicity of pegloticase will be assessed in serum samples by evaluating anti-PEG and anti-uricase IgG antibodies. Samples will be collected prior to the pegloticase infusion on Day 1 and at the Weeks 2, 6, 12, 20 and the End-of-study (Week 24)/Early Termination Visit and 3-month Post-Treatment Follow-up Visits. In the event of an AE suspected to be an IR, a serum sample will be collected at that time or at the subsequent visit for evaluation of pegloticase/PEG antibodies.

For anti-PEG IgG antibodies, using the safety analysis set, the number and percentage of subjects who meet the following criteria will be summarized by scheduled timepoint and overall:

- ADA positive at pegloticase baseline
- ADA negative at pegloticase baseline
- ADA negative at pegloticase baseline and ADA positive at post-pegloticase baseline
  - ADA positive at pegloticase baseline with increase in titer from pegloticase baseline
  - ADA negative at pegloticase baseline and ADA positive at post-pegloticase baseline or with increase in titer from pegloticase baseline (i.e. ADA positive status post-baseline)

For anti-uricase IgG antibodies, the number and percentage of subjects with ADA positive at pegloticase baseline and post-pegloticase baseline will be summarized by scheduled timepoint.

Kaplan-Meier estimates of the time to positive anti-PEG response (for subjects who were negative at baseline) or increase in anti-PEG titer (for subjects who were positive at baseline), and the time to anti-uricase response with 25th percentile, median, 75th percentile, and 95% CI, along with a Kaplan-Meier curve will be produced. Subjects who never have a positive anti-PEG response or increase in titer will be censored at the date of their last visit (3 month follow up visit, or, if the subject did not attend this visit, then whatever last visit they have on record). Antibody result from both scheduled and unscheduled visits will be included for the time to event analysis.

Anti-PEG and anti-uricase titer will be summarized descriptively with mean and CV% by study visit. Additionally, Anti-PEG titers at the last pegloticase infusion and post-treatment will be summarized for ADA positive post-baseline subjects.

All results will be presented by ‘as assigned’ infusion duration group.

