### 3.6.3.4 AEs of Special Interest

Incidence of IRs, anaphylaxis, gout flares and Major Adverse Cardiovascular Events (MACE) will be summarized for the safety analysis set by infusion duration group. Separate summaries will be produced for adjudicated events and reported events (only applies to IRs, anaphylaxis and MACE events – gout flares are not adjudicated).

Summaries of IRs and anaphylaxis will group events by 3 categories:

- Anaphylaxis
- Infusion reactions including anaphylaxis
- Infusion reactions excluding anaphylaxis

Both the investigator-reported and adjudicated events and the associated signs and symptoms will be summarized separately by severity, and the time relative to the most recent pegloticase infusion for each category above. Signs and symptoms will also be summarized by SOC and PT.

Time relative to the most recent pegloticase infusion will be categorized as: during infusion,  $\leq 2$  hours after infusion,  $> 2$  hours to 24 hours after infusion, and  $> 24$  hours after infusion. If the time of the infusion reaction or anaphylaxis is missing, the category will be assigned as “Missing”.

Serious events and the associated symptoms will be summarized by SOC and PT for each category.

The number of events per subject per treatment infusion duration group, the number of events and serious events per infusion, and the number of subjects with the first event by infusion number will be summarized as well for each category. IRs (including anaphylaxis) that occur on the same date will be considered one event.

In addition, the number and percentage of subjects with adjudicated IRs, including anaphylaxis, will be summarized by severity of event using the following categories for both anti-PEG and anti-uricase antibodies:

- ADA status at baseline (positive or negative)
- ADA status post-baseline (positive or negative)
  - ADA positive post-baseline: negative at baseline and positive at any post-baseline time point, or positive at baseline and with an increase in titer at post-baseline timepoint
  - ADA negative post-baseline: defined as negative at all time points, or positive at baseline and without post-baseline increases in titer from baseline titer

MACEs are defined as: including non-fatal myocardial infarction, non-fatal stroke, cardiovascular death, and congestive heart failure. The following search algorithm will be used to identify possible MACEs:

- For cardiovascular death: any fatal cases with following terms

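### Any rise in titer over a single baseline reading makes a baseline-positive subject ADA positive post-baseline, so assay scatter alone can set the label, by an amount the documents do not allow us to fix

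*SAP*

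**What the plan says.** SAP 3.6.3.4 defines post-baseline ADA status for anti-PEG and anti-uricase antibodies. A subject already positive at baseline becomes post-baseline positive if "or positive at baseline and with an increase in titer at post-baseline timepoint" applies. The negative class takes subjects negative throughout, "or positive at baseline and without post-baseline increases in titer from baseline titer". Read together, a single rise of any size in any later sample moves a baseline-positive subject out of the negative class.

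SAP 3.5.2 uses the same idea for anti-PEG. Its table has a row for "ADA positive at pegloticase baseline with increase in titer from pegloticase baseline", reported by scheduled timepoint and overall, and one Kaplan-Meier event is "increase in anti-PEG titer (for subjects who were positive at baseline"). Neither place gives a minimum rise.

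The label is used in two further summaries: adjudicated infusion reactions (IRs) by severity in SAP 3.6.3.4, and response in SAP 3.4.2.1, where "The proportion of Month 6 responders by pegloticase baseline and post baseline ADA (positive /negative) status will be summarized", with a pointer to 3.6.3.4 for the definition.

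On sampling, SAP 1.4.2 says: "Samples will be collected prior to the pegloticase infusion on Day 1 and at the Weeks 2, 6, 12, 20 and the End-of-study" (Week 24), the last of these shared with the "Early Termination Visit and 3-month Post-Treatment Follow-up Visits". It adds: "In the event of an AE suspected to be an IR, a serum sample will be collected at that time or at the subsequent visit". Under SAP 3.1.3 the pegloticase baseline is the last non-missing value before the first infusion, so it is one reading.

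**The concern.** The comparison is lopsided: the highest of several later readings is set against one baseline reading that carries its own error. Even if nothing changes biologically, the maximum of several noisy readings tends to exceed a single noisy reading, and more samples make this more likely.

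This matters because immunogenicity is the programme's own explanation for IRs and loss of response. Protocol 7.1.2 supports that explanation with a high-titer cut (above 1:2430): IRs in 60% versus 19%, and maintained response in 2% versus 63%. A label that fires on any increase ignores the size of the rise and mixes trivial fluctuation with real boosting. The IR and Month 6 response tables by ADA status, the overall row for titer increase and the time-to-ADA curve would all carry that mixture.

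The error need not be equal across outcomes. Under protocol 9.3 and 9.4.3, subjects taken off pegloticase stay for follow-up visits only and can miss ADA samples, while a suspected IR can add one.

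**Working it through.** The plan states no error rate for this label, so there is no figure of its own to reproduce.

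**Inputs**

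- Scheduled post-baseline samples (SAP 1.4.2): Weeks 2, 6, 12, 20 and 24 plus the 3-month visit, so k = 6 with full attendance. A suspected-IR sample makes k = 7 unless it coincides with a scheduled one. A subject who stops early may have about k = 3.
- Baseline: one reading (SAP 3.1.3).
- Assay precision and dilution step: not given. Everything below is therefore a range under assumptions, for a baseline-positive subject with no true change.

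**1. Continuous titers, no ties.** All k + 1 readings are exchangeable, so the chance that the baseline is not the highest is k/(k + 1). For k = 6 this is 6/7 = 86%. It is the upper end.

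**2. Fixed chance p that one later sample reads above baseline, samples treated as independent.** The chance of at least one is 1 − (1 − p)^k. For k = 6:

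| p | 1% | 2% | 5% | 10% | 15% | 20% |
|---|---|---|---|---|---|---|
| label | 6% | 11% | 26% | 47% | 62% | 74% |

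The 50% point is p = 1 − 0.5^(1/6) = 10.9%. The later readings share one baseline, which makes the comparisons positively dependent and lowers the chance of at least one. So 10.9% is a necessary condition for reaching half, not a sufficient one.

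**3. One-step error.** Each reading, baseline included, is one dilution step too high with probability q and one too low with probability q.

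- Any increase: q(1 − q^k) + (1 − 2q)(1 − (1 − q)^k)
- Rise of at least two steps: q(1 − (1 − q)^k)

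For q = 0.10 and k = 6, any increase: 0.10 + 0.80 × (1 − 0.531) = 0.475. Two steps: 0.10 × (1 − 0.531) = 0.047.

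| q | any increase, k = 6 | any increase, k = 3 | two steps, k = 6 |
|---|---|---|---|
| 0.05 | 29% | 18% | 1% |
| 0.10 | 47% | 32% | 5% |
| 0.15 | 59% | 42% | 9% |
| 0.20 | 64% | 49% | 15% |

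At q = 0.10 the false-label rate is thus 32% with three samples and 47% with six. With seven it is 0.10 + 0.80 × (1 − 0.9^7) = 0.10 + 0.80 × (1 − 0.478) = 52%. This is how it can differ between early stoppers, completers and subjects with a suspected IR.

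**4. Normal log-titer scatter of s steps, read on a dilution grid** (simulation, 400,000 subjects, k = 6). Any increase: 14% at s = 0.1, 27% at 0.2, 40% at 0.3, 50% at 0.4, 58% at 0.5 and 73% at 1.0. At s = 0.4 a single later sample exceeds baseline with probability about 22%, so with a shared baseline the requirement for reaching half is well above 10.9%. In terms of assay CV, with s = √ln(1 + CV²) / ln(dilution factor):

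| CV | two-fold steps | three-fold steps |
|---|---|---|
| 10% | 19% | 12% |
| 20% | 38% | 24% |
| 30% | 52% | 36% |
| 50% | 66% | 53% |

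A two-step rule gives under 0.1% at s = 0.2, 4% at 0.4, 10% at 0.5 and 42% at 1.0.

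**5. What a threshold loses.** Take a true one-step rise present at all six later samples, under the model in step 3. A two-step rule detects it with probability q(1 − q^6) + (1 − 2q)(1 − (1 − q)^6), the same expression as the any-increase false-label rate. It therefore misses 71%, 53%, 41% or 36% at q = 0.05, 0.10, 0.15 or 0.20. The any-increase rule misses q(1 − q)^6 + (1 − 2q)q^6, about 4% to 6%.

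**The case against.** **A reader might infer that about half or more of unchanged subjects will be mislabelled.** The documents do not support that as a general figure. They give neither precision nor dilution step. The one titer quoted, 1:2430 in protocol 7.1.2, equals 10 × 3^5 and so fits a three-fold series. It comes from the earlier phase 3 studies and is only a hint, but with three-fold steps half is passed in the table above only at a CV of 50%. Six samples is also a maximum of the scheduled count: with three, the step model stays below half for every q shown. This objection stands.

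**A reader might also infer that the reported incidence of boosting is materially too high, that the outcome contrasts are diluted toward no difference, or that the time-to-event curve mostly mirrors the visit schedule.** None of these can be sized, because neither the share positive at baseline nor the share with no true change is given. With sample counts that depend on outcome, the distortion need not run toward no difference. Antibody detected at fixed visits follows the visit schedule under any threshold. Unscheduled samples are explicitly included only for the time-to-event analysis in SAP 3.5.2, not for the label in 3.6.3.4.

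**For a safety summary, sensitivity may reasonably be preferred.** This stands in part. A two-step rule has a real cost (step 5), and in a three-fold series it demands a nine-fold rise. That argues for a threshold tied to the assay and for showing both versions. It does not argue for leaving the threshold unstated.

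**The plan already offers partial cover and the stakes are limited.** SAP 3.5.2 gives baseline-positive subjects with a rise their own row and summarizes titers by visit, and SAP 3.1.1 provides listings. SAP 3.1.1 also rules out inferential testing, and the antibody objective is exploratory. All true, and it lowers the priority. It does not repair the two-way split in the IR and Month 6 tables, where seroconverters and any-increase subjects share one class.

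**A minimum significant ratio may exist in the Laboratory Manual or an assay validation report.** Those are outside the two documents. If so, the SAP need only refer to it.

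**Conclusion.** The definition has a real but bounded weakness. As written, it can label a baseline-positive subject with no true change as ADA positive post-baseline through assay scatter alone, and the chance rises with the number of samples. Across reasonable assumptions it is roughly 10% to 85% with six later samples, and lower still if the assay almost always reproduces the same titer. Half or more requires a chance of at least about 11% that a single later sample reads above baseline, and more than that once the shared baseline is allowed for.

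The range rests on assumed scatter and applies only to baseline-positive subjects without real change. The effect on the whole tables cannot be sized from the documents. The false-label rate can differ by outcome because early stoppers may have fewer samples and a suspected IR can add one. The analyses affected are descriptive: IRs by ADA status, Month 6 response by ADA status, the overall anti-PEG titer-increase row and the anti-PEG Kaplan-Meier event. The primary endpoint and the Month 6 responder definition do not use the label.

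**What to change.** In SAP 3.5.2 and 3.6.3.4:

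1. Count a baseline-positive subject as boosted, and so post-baseline positive, only if a post-baseline titer exceeds baseline by at least the assay's validated minimum significant ratio. If no such ratio is available, use two dilution steps.
2. Define the baseline-positive part of the ADA negative post-baseline class as the complement of that rule.
3. Use the same threshold for the Kaplan-Meier event in subjects positive at baseline.
4. Report the any-increase version alongside as a sensitivity summary.

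The Month 6 response table then follows through its pointer to 3.6.3.4.

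The cost is a change of SAP wording, one derivation and one extra set of summaries, with no new samples. The downside is that the thresholded label misses small true rises: with the two-step fallback, about 36% to 71% of sustained one-step rises at q = 0.20 to 0.05 in the step-error model. That is the reason to keep the any-increase summary beside it.

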### 3.4.3 Exploratory Endpoint Analyses

## 3.5 Analysis of Pegloticase Pharmacokinetics, Methotrexate Polyglutamates, and Anti-Drug Antibodies

### 3.5.1 Pegloticase and MTX PK

Serum samples for pegloticase PK analysis will be collected approximately 15 minutes to 2 hours after the end of infusion on Day 1; prior to infusion and approximately 15 minutes to 2 hours after the end of the infusion at Weeks 2, 6, 12 and 20. An additional PK sample will be collected at the End-of-Study (Week 24)/Early Termination Visit.

PK summaries will be done for the PK analysis set. MTX polyglutamate summaries will be done for the mITT analysis set. All results will be presented by 'as assigned' infusion duration group.

The following presentations of subject serum pegloticase concentration data covered in this SAP will be provided for pegloticase:

- A listing including subject, week/time point (actual, planned), treatment and serum concentrations. End of infusion sampling times are expressed relative to the start time of infusion.
- A table summary of serum pegloticase concentrations at each time point (n; mean, SD, coefficient of variation (CV)% calculated as  $100\% \times SD/mean$ , minimum, 25th percentile, median, 75th percentile, maximum, geometric mean and geometric CV%) will be provided for the PK analysis set. Similar tables will be produced by Month 6 sUA responder status.

Further, the mean and CV% of pegloticase concentrations will be provided by visit in the subset of subjects who are ADA positive (defined as positive for anti-PEG or anti-uricase antibodies at any visit) and ADA negative (defined as negative for both anti-PEG and anti-uricase antibodies at all visits) for each visit.

All concentrations BLQ after the first pegloticase infusion will be imputed by half of LLOQ for the analysis summaries. The number of BLQ records will be summarized. Concentrations more than 17 days after the last infusion will be excluded from the summary.

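### SAP 3.6.3.4 counts baseline-positive subjects without a titer rise as ADA negative post-baseline, which hides their IR and response rates and does not match the PK subsets

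*SAP*

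**What the plan says.** Three sets of SAP tables sort subjects by anti-drug antibody (ADA) status.

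- **PK concentrations (SAP 3.5.1).** One group is "ADA positive (defined as positive for anti-PEG or anti-uricase antibodies at any visit"; the other is "ADA negative (defined as negative for both anti-PEG and anti-uricase antibodies at all visits". The baseline sample counts, the two antibodies are combined, and titer plays no part.
- **Adjudicated IRs (SAP 3.6.3.4).** The split is made "using the following categories for both anti-PEG and anti-uricase antibodies". There is a baseline split, "ADA status at baseline (positive or negative", and a post-baseline split. The upper category of the latter is "ADA positive post-baseline: negative at baseline and positive at any post-baseline time point, or positive at baseline and with an increase in titer"; the lower is "ADA negative post-baseline: defined as negative at all time points, or positive at baseline and without post-baseline increases in titer from baseline titer".
- **Month 6 response (SAP 3.4.2.1).** "The proportion of Month 6 responders by pegloticase baseline and post baseline ADA (positive /negative) status will be summarized similarly as the above". For the definitions the section points elsewhere: "Please see Section 3.6.3.4 for the definition of pegloticase baseline and post baseline ADA status".

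SAP 3.5.2 adds the antibody summaries themselves. For anti-PEG it uses the same new-or-boosted idea as 3.6.3.4. For anti-uricase it counts plain positivity at baseline and afterwards, with no titer condition.

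**The concern.** A rise from baseline is a sensible way to define treatment-emergent antibody. Its complement, however, is not absence of antibody. Under 3.6.3.4 the row labelled negative holds two kinds of subject: those who never had antibody, and those who had it at baseline and may have kept it throughout at an unchanged titer. No table shows IR or response rates for the second kind alone.

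Two things are at stake. If stable carriers do worse than never-positive subjects, pooling them with that comparator weakens the ADA contrast for IRs and for Month 6 response. And a reader who sets the PK concentrations by ADA status beside the IR and response tables will be comparing different sets of subjects under similar names. SAP version 2.0 added the response and IR summaries by ADA status, so they are there to be read.

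**Working it through.** The plan gives no figure on this point, so there is none to reproduce. The check has three parts.

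**1. Apply both rules to every titer pattern.** Take one antibody, a baseline sample and three later samples, each with titer level 0 (negative), 1 or 2. That gives 3^4 = 81 patterns.

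- PK rule (3.5.1): positive if any of the four samples is above 0.
- Post-baseline rule (3.6.3.4): positive if baseline is 0 and any later sample is above 0, or if baseline is above 0 and any later sample exceeds it. Otherwise negative.

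| Baseline level | Negative under both | Positive under both | PK positive, negative post-baseline |
|---|---|---|---|
| 0 | 1 | 26 | 0 |
| 1 | 0 | 27 − 8 = 19 | 2^3 = 8 |
| 2 | 0 | 0 | 27 |
| Total | 1 | 45 | 35 |

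All 35 discordant patterns are baseline positive without a rise. In 2 of them (one for each positive baseline level) every later sample is negative, so the post-baseline label is literally true. The other 33 have at least one later positive sample, and 1 + 2^3 = 9 are positive in every sample. These are counts of possible patterns on an arbitrary grid, not expected numbers of subjects.

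**2. Follow one subject through the tables.** Take a subject positive in every sample with a flat titer.

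| Table | Status of this subject |
|---|---|
| PK concentrations, 3.5.1 | ADA positive |
| IRs and Month 6 response, baseline split | positive |
| IRs and Month 6 response, post-baseline split | negative |
| Anti-PEG summary, 3.5.2 | positive at baseline; not in the post-baseline positive row |
| Anti-uricase summary, 3.5.2 | positive at baseline and afterwards |

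The titer rule is not the only source of mismatch. A subject who is anti-PEG negative throughout but becomes anti-uricase positive is ADA positive in the PK split and negative post-baseline for anti-PEG. Section 3.4.2.1 does not say whether response is split by each antibody or by a combined status.

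**3. Size of the dilution in the response contrast.** The documents give no prevalence of baseline antibody, no share without a rise, no conversion rate and no response rate by these groups. All inputs below except the 110 are assumptions.

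- Subjects in the selected cohort: 110 (SAP 1.1.3).
- Baseline positive: b = 10% to 40%, half of them without a titer rise.
- Baseline negatives who convert: 20%.
- Response: 85% in never-positive and 40% in treatment-emergent subjects, so the undiluted contrast is 45 points.
- Response in stable carriers: r, from 40% to 85%.

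Stable = 110 × b × 0.5. Never positive = 110 × (1 − b) × 0.8. Share = stable / (stable + never). Dilution = share × (85 − r) points.

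| b | Stable | Never | Share | Response in pooled row, r = 40% | Contrast, r = 40% | Dilution, r = 40% | Dilution, r = 85% |
|---|---|---|---|---|---|---|---|
| 10% | 5.5 | 79.2 | 6.5% | 82.1% | 42.1 | 2.9 | 0 |
| 20% | 11.0 | 70.4 | 13.5% | 78.9% | 38.9 | 6.1 | 0 |
| 30% | 16.5 | 61.6 | 21.1% | 75.5% | 35.5 | 9.5 | 0 |
| 40% | 22.0 | 52.8 | 29.4% | 71.8% | 31.8 | 13.2 | 0 |

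The range is 0 to about 13 points, and r decides where in it the result falls. No comparable figure is offered for IRs. At the planning rate of 5%, 110 × 0.05 = 5.5 subjects would have an IR, too few to split further by severity and ADA status with any stability under either rule.

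**The case against.** The strongest reply is that these are two variables, not two definitions of one. Section 3.5.1 speaks of ADA positive; 3.6.3.4 speaks of ADA positive or negative post-baseline. Each rule is written out, and 3.4.2.1, 3.6.3.4 and the anti-PEG part of 3.5.2 agree with one another. That stands: a reader might infer that the SAP contradicts itself or leaves ADA status undefined, and it does neither. The fault is one of labelling and comparability.

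Second, stable carriers are not invisible. The baseline split shows them as positive, and for anti-PEG their number follows from 3.5.2 by subtracting baseline positives with a rise from all baseline positives, where sampling is complete. That also stands. What it does not give is their IR or response rate, because the SAP does not cross baseline with post-baseline status.

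Third, a reader might infer from Protocol 7.1.2 that stable carriers are known to do badly. The figures there (response 2% versus 63%, IRs 60% versus 19%) set subjects with titers above 1:2430 against subjects without such high titers. As worded, both comparators can include low-titer positives. They support concern about a high titer that stays high, not about any stable positivity, and so do not justify fixing r at 40%.

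Last, immunogenicity is an exploratory objective and the SAP plans no inferential testing. That limits the weight of the point but does not remove it.

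**Conclusion.** The point holds as a labelling and comparability fault in descriptive tables. Under 3.6.3.4, and through it 3.4.2.1, baseline-positive subjects without a titer rise are pooled with never-positive subjects. Section 3.5.1 counts the same subjects as ADA positive, and no planned table isolates their outcomes.

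The size of any dilution cannot be computed from the documents. Under the assumed inputs it runs from 0 points, if stable carriers respond like never-positive subjects, to about 13 points, if 40% are baseline positive and stable carriers respond like treatment-emergent ones. A reader might take the upper end as an expected bias; nothing in the documents supports that. Nor does the point reach the primary endpoint, its 13% criterion or the overall Month 6 response rate, none of which uses ADA status.

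The change is worth making because it is cheap and uses data already collected, not because a conclusion of the trial depends on it.

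**What to change.** - In 3.6.3.4 and 3.4.2.1, report IRs and Month 6 response for each antibody in three rows: never positive; baseline positive without a titer rise; treatment-emergent (negative then positive, or positive with a rise). Say what counts as a rise, since the SAP sets no minimum.
- If two groups are kept, label them treatment-emergent ADA yes and no, not positive and negative.
- In 3.5.1, build the PK subsets from the same per-antibody variable, or state a rule for combining anti-PEG and anti-uricase. Without one of these the PK groups will still differ from the others.
- In 3.5.2, apply the same variable to the anti-uricase summary.

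The cost is SAP wording, one derived variable per antibody and one extra row per table. No new data are needed, and SAP 3.1 provides for changes before database lock by SAP amendment. The downside is small cells in the stable-positive row, above all for IRs, which should be shown as counts and not over-read.
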